2.2 ENDPOINTS

2.2.1 Primary Endpoint

1. Correct history taking of case of pneumonia
2. Correct examination of case of pneumonia
3. Correct diagnosis of case of pneumonia
4. Correct treatment of case of pneumonia

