and KPK will have one training as their participants can be managed to be brought in one location due to close proximity. Sindh and Baluchistan participants will have two separate trainings.

3.5 Recruitment of Disguised Patients' Caregiver and Conduction of Observations:

Each data collector will be provided a pre-defined list of addresses whereby the observations will be made. He/she will go to the location and will search the nearby community for cases of pneumonia in children under five. Once the cases have been identified, their caregivers will be sought. These caregivers are the primary individuals providing direct care to the child. Usually, these are the mothers, fathers, grandmothers or guardians of the child. They will explained the purpose of the study and will be requested to participate in the study by acting as disguised caregivers to accompany the data collector to the health facilities and upon agreement will sign a consent form. This means that they will disguise as an acquaintance of the data collector who will take them to the healthcare professional to be observed. They will take the ill child along, give the history of that child to the healthcare professional and answer any relevant questions which will be asked by him/her and get the child examined and treated. In the meantime, the data collector will make the relevant observations based on the observation tool which will be filled after the visit. The data collector will not reveal that he/she is a healthcare professional. Additionally, the data collector will also take an audio recorder along to record the entire conversation which will help in filling up the observation tool later and also validate the visit. Once the visit is completed, the data collector will take the caregiver back to their premises and fill up the observation tool in tablets within one hour of the visit.

3.6 Project work-plan:

PROJECT ACTIVITIES	YEAR 1(Months)												YEAR 2
	1	2	3	4	5	6	7	8	9	10	11	12	
Ethical Clearance	X	X											
Staff Recruitment		X											
Tool Development			X										
Inception Meetings for development of implementation strategies			X										
Pretesting and Finalization of the tool				X	X								
Data Collections (Trainings, identification of study site/centers, observations)				X	X	X	X	X	X				
Data Analysis & Reporting										X	X	X	X

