7 DATA COLLECTION

Data will be collected in the form of observations and then entered upon leaving the facility within one hour of the observation. For the purpose of ensuring accurate data entry, the data collector will use the audio recording and the prescription, the copy of which will be kept with them.

A detailed checklist will be used to assess the adherence of the healthcare providers to standard guidelines. This checklist will include all aspects covered in section 6.1:

- ✓ History taking
- ✓ Examination
- ✓ Diagnosis
- ✓ Treatment/management

These areas encompass the guidelines of essential care for pneumonia. Here essential care refers to the questions providers must ask the caregiver and examinations provider must conduct to accomplish correct diagnosis.

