7.1 Source Data Documentation

The checklist will be developed in the form of a structured Urdu questionnaire which will be pretested. It will then be transformed into a soft version using our online questionnaire development dashboard. The questionnaire will then be installed into tablets.

Data will be collected in tablets to avoid errors of skips and logic. It will have an essential component of not accepting incomplete forms which will ensure that complete data is being collected on site. This data will be sent to our headquarters from all over the country via online server. This will ensure rapid access to data and data confidentiality as it will only be accessed by our data manager located in the headquarters through a password restricted data dashboard.

Each data collector will be provided a tablet, its charging cable and a power-bank to ensure that the tablet is charged all the time. In case any technical error is faced in any of the tablets, he/she will inform the supervisor who will arrange an alternate tablet to enter data. Additionally, the data collector will also have extra hard copies of the questionnaires to enter data in case a technical error occurs in the tablet and if there is a delay in delivery of an alternate one. These hard copies will be sent to the project manager via courier on the same of completion of data collection to avoid delay in data entry. The data collector will also maintain a contact sheet which will include information on the location, date and time of the observation, name of the child and caregiver, phone number, observed health professional's name and level of health facility/care.

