8.2 PROPOSED ANALYSES

Behavioural coding will be employed to prepare the data for analysis. This means that a predetermined code will be given to each variable against each category of observations (History, examination, diagnosis and treatment). Each variable will be answered as "Y" meaning yes, the task was accomplished and "N" meaning no, the task was not accomplished (section 6.1). Additionally, the responses will be labelled as correct, partially correct and incorrect for history taking and examination. If on history taking, the healthcare provider asks questions on all variables, then the responses will be labelled as correct and if any one variable is missed then the response is indicated as partially correct and in case less than 50% of the variables are asked about, then the responses will be labelled as incorrect. The same labels will be specified for the examination. In case of diagnosis and treatment, the labels will be specified as correct and incorrect only as there is no partially correct diagnosis and treatment regimens. The overall frequencies and percentages of these responses will be calculated and cross tabulated across the provinces.

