ANNEX C- OBSERVATION TOOL

CLINICAL OBSERVATIONS (were the following parameters followed)	
1. History taking	Y/N
Cough	
Fast breathing	
Laboured breathing	
Fever	
Immunization	
Breastfeeding history	
Overcrowding	
Parental smoking/Household member smoking	
Air pollution (indoor cooking stove)	
Nutritional history	
Hygienic practices	
Family history of HIV	
2. Examination (Did the healthcare provider make the following necessary examinations apart from others)	
Temperature	
Respiratory rate counting for 1 minute	
Pallor	
Skin rash	
Examine lower chest in drawing	
Auscultate for wheeze or crepts	
3. Diagnosis (Did the healthcare provider make the correct diagnosis based on WHO guidelines)	
Cough with no fast breathing/chest in drawing: No pneumonia	
With fast breathing and/or chest in drawing : Pneumonia	
Pneumonia with any danger signs : Severe Pneumonia	
4. Management (Did the healthcare provider manage the case per the guidelines)	

No Pneumonia: Symptomatic treatment	
Pneumonia: Oral amoxicillin 40mg/kg/dose twice daily for three days	
Severe Pneumonia: For LHWs: First dose of oral antibiotic (amoxicillin) and referral to health facility and For BHUs: First dose of oral antibiotic (amoxicillin) and referral to rural health centre or tertiary care hospital For health facilities (public and private) : Parenteral ampicillin 50mg/kg IV 6 hourly for five days along with gentamicin 7.5mg/kg/ IM or IV for five days.	

SCORE: (Count the total number of Y and enter the value in the table below)

ACTIVITY OBSERVED	“ Y” SCORED	TOTAL
History Taking		12
Examination		6
Diagnosis		1
Management		1

OBSERVATION RESULT*:

ACTIVITY OBSERVED	SELECT THE APPROPRIATE RESPONSE
History Taking	Correct/partially correct/ incorrect
Examination	Correct/partially correct/ incorrect
Diagnosis	Correct/ Incorrect
Management	Correct/ Incorrect

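### Primary endpoint 3 has no code for a visit with no spoken or written diagnosis, so silence is scored as diagnostic error or guessed

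*Combined protocol and SAP*

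**What the plan says.** - **Endpoint.** Section 2.2.1 lists "Correct diagnosis of case of pneumonia" as the third of four primary endpoints; treatment is the fourth.
- **Conduct of the visit.** In section 3.5 the caregiver takes the child along, gives the history and is to "answer any relevant questions which will be asked by him/her and get the child examined and treated". Meanwhile "the data collector will make the relevant observations based on the observation tool which will be filled after the visit". The disguise is kept: "The data collector will not reveal that he/she is a healthcare professional". The visit is audio recorded.
- **Sources for the form.** For accurate entry, section 7 says that "the data collector will use the audio recording and the prescription". The eCRF list in section 7.2 has a picture of the prescription, but no field for the diagnosis as the provider stated it.
- **Scoring.** Section 8.2 codes every variable Y or N, with N for a task left undone. For diagnosis, "the labels will be specified as correct and incorrect only". Annex C asks "Did the healthcare provider make the correct diagnosis based on WHO guidelines" and scores the answer 1 or 0.
- **Blanks.** Section 7.1 describes a tablet form "not accepting incomplete forms which will ensure that complete data is being collected on site".

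**The concern.** In a disguised observation the provider's conclusion is visible only if it is said or written. Some providers will examine, prescribe and close the visit without naming the illness. The plan has no category for that visit and the form cannot be left blank, so the data collector has two options:

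1. Code N. A provider who reached the right diagnosis silently is counted with one who misdiagnosed.
2. Guess. The prescription is the obvious clue. A diagnosis deduced from the drug carries no information beyond endpoint 4, so the two primary endpoints are no longer separate measures for those visits.

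The first option changes what endpoint 3 means. Annex C asks whether the provider made the correct diagnosis, and no item scores telling the caregiver. Under option 1 the endpoint mixes diagnostic correctness with the habit of voicing or writing the diagnosis. That habit may differ between an LHW's home visit, a BHU and a tertiary outpatient department, so the rates by level of care, which the primary objective is about, could differ for reasons other than diagnosis.

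**Working it through.** **1. The plan's own figures.** Section 8.1: 6 + 4 + 4 + 9 + 9 = 32 observations per location; 32 × 5 = 160. Both reproduce. Totals by level are 30 LHW, 20 BHU, 20 RHC, 45 private and 45 public. The plan states no expected rate for endpoint 3 and no rate of unstated diagnoses.

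**2. Is there any route for an unstated diagnosis?** Section 3.5 has no instruction to ask and no later contact with the provider. Section 7.2 has no field for the stated diagnosis. Annex C item 3 has no *not stated* option, and its closing free-text line does not enter the score. Section 8.2 permits two labels and section 7.1 permits no blank. The text contains no such route.

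**3. Silence coded incorrect.** Let *p* be the share truly correct and *u* the share of visits with no stated diagnosis, with silence unrelated to correctness. Both values are assumed. Recorded rate = *p* × (1 − *u*). With *p* = 0.60:

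| *u* | Coded incorrect | If every silent visit were coded correct |
|---|---|---|
| 10% | 0.60 × 0.90 = 54% | 0.54 + 0.10 = 64% |
| 40% | 0.60 × 0.60 = 36% | 0.36 + 0.40 = 76% |

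The last column is an upper bound, reached only if every silent visit had a drug that matched. The gap between the columns equals *u*, whatever *p* is.

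**4. Sensitivity to *p*.** With *p* = 0.70, silence of 10%, 20%, 30% and 50% gives 63%, 56%, 49% and 35% when coded incorrect, and at most 73%, 76%, 79% and 85% when coded correct.

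**5. Against sampling error.** At 70% and n = 160 the Wilson 95% interval is 62.5% to 76.6%, a width of 14.1 points. The gap between the two codings is 10 points at 10% silence, inside that width, and 20 points at 20% silence, outside it.

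**6. Levels and provinces.** If two levels have the same *p* = 0.60 but *u* = 10% and 40%, they read 54% and 36%, a false gap of 18 points. For provinces, section 8.1 gives each location the same mix, with weights 6/32, 4/32, 4/32, 9/32 and 9/32. If silence depends on level only, equally skilled provinces lose the same amount, and no false difference between them arises.

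**The case against.** **N is a defensible reading.** Section 8.2 codes N for a task not done, and the study is about actual practice, not latent skill. Whether silence should count against the provider is a choice of construct. That is fair, but the plan does not state the choice. Annex C words the item as making the diagnosis, and a single N cannot show how much is error and how much is silence.

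**The tool is not final.** Section 3.1 provides for an advisory committee, section 3.4 for training with mock exercises, and section 3.6 for pretesting in months 4 and 5. These, or pages not available here, could close the gap. The text available does not say that they do.

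**Stronger readings that the documents do not support:**

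- *The diagnosis is never elicited.* The caregivers are real carers of ill children and may ask unprompted. Elicitation is unspecified, not excluded.
- *The plan infers diagnosis from the drug.* Section 7 names the prescription as a source for data entry; no rule says the diagnosis is deduced from it. This is a risk.
- *The damage is irreversible.* Recordings are kept for at least three years (section 11.4), so visits can later be recoded as stated or not stated. Only the unspoken diagnosis is lost.
- *The provincial comparison is biased.* Level-dependent silence alone does not do this (step 6). Silence or coding habits would have to differ by province within a level, and nothing in the documents shows that.
- *The artefact between levels is 18 points.* The 10% and 40% are assumptions. At 30 LHW and 45 public observations, the 95% half-width for 54% versus 36% is 1.96 × √(0.54 × 0.46/30 + 0.36 × 0.64/45) ≈ 23 points, so a gap of that size would lie within sampling error.

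**Conclusion.** The point holds. Under the binary rule, a visit without a spoken or written diagnosis is either merged with misdiagnosis or guessed, and this affects a primary endpoint. The overall and level-specific rates for endpoint 3 can be distorted.

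The size is unknown. The range of 54% to 36% against a true 60% rests on three assumptions: 10% to 40% unstated, silence independent of correctness, and all silent visits coded incorrect. The documents confirm none of them. They also do not establish which level would be quieter, that provinces are biased, or that collectors will work back from the drug. The change should be made before the tool is finalised, because the audio can later identify the silent visits but not what the provider thought.

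**What to change.** - **Annex C item 3 and section 8.2.** Add a *diagnosis not stated* code. Record the diagnosis as stated and its source (spontaneous speech, written, or elicited). State that the diagnosis may not be inferred from the drug.
- **Section 8.2, reporting.** Give endpoint 3 among all visits, with not stated counted as not correct, and among visits with a stated diagnosis. Show the not-stated percentage by level and province. Both denominators are needed, since dropping silent visits may itself select.
- **Section 3.5.** Add one fixed, neutral closing question from the caregiver on what illness the child has, asked after treatment is given or prescribed. Keep the elicited answer separate from any spontaneous one, so that undisturbed practice can still be reported.

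**Cost.** One line in the caregiver briefing and a few fields on the tablet form, before a pretest that is already scheduled. There are two downsides. The question may prompt a diagnosis the provider had not formed; asking it last and recording the source limits this. Where one caregiver goes on to an LHW, a BHU and an RHC (section 4.1), an answer from the first visit may reach the next provider through the history. Later visits by the same caregiver should be flagged, and results also shown without them.

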The FLCF level will include observations made at the primary health care facilities which are the Basic Health Units (BHUs) and Rural Health Centres (RHCs). A basic health unit is located within a union council which is the smallest administrative unit in the Pakistani administrative system. Each basic health unit covers a catchment area of 25,000 households. Pakistan has around 5,290 BHUs although not all are functional. Services provided at BHU are promotive, preventive, curative and referral .LHWs refer patients usually to BHUs. RHCs provide in-patient service as compared to BHUs. They usually have 10-20 beds and cover a catchment area of 100,000 people. The RHC provides promotive, preventive, curative, diagnostics and referral services apart from the in-patient services. It also provides clinical, logistical and managerial support to the BHUs, LHWs, and dispensaries that fall within its geographical limits. RHC also provides medico-legal, basic surgical, dental and ambulance services. There are around 552 RHCs in Pakistan.

The practitioner level observations will include those of practitioners at both the private and public sector. The public sector will include observations made in outpatient departments of selected tertiary care hospitals across the study sites. Observations made at the private practitioner level will include selected solitary private clinics or clinics within private hospitals. The community and FLCF level will represent practices within the rural community and the practitioner level will represent practices within the semi urban/urban communities.

3.3 Type of Observations:

These will be participant, structured, disguised observations which will be done using a validated observation tool based on standard WHO pneumonia case management guidelines, developed in close collaboration with experts from University of Edinburgh. This tool will be pretested and translated into Urdu.

3.4 Data Collectors:

A team of data collectors, who will be healthcare professionals, will be trained on appropriate administration of the observation tool upon recruitment. The training will also include an introduction to pneumonia, its signs and symptoms, diagnosis and management according to WHO guidelines. A 3 day interactive training workshop will be conducted whereby mock excesses will also be conducted. A total of three trainings will be conducted whereby data collectors from Islamabad (capital), Punjab

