4.2 INCLUSION CRITERIA

4.2.1 INCLUSION CRITERIA OF DISGUISED CAREGIVERS:

- Caregivers of children under five years of age. These are those individuals who provide direct care to the child. These could either be a mother, father, grandmother or guardian.
- The child under five under that caregiver's household must have symptoms of pneumonia/severe pneumonia as indicated in section 6.1
- Caregivers consenting to be a part of the study.

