5 PARTICIPANT SELECTION AND ENROLMENT

5.1 IDENTIFYING PARTICIPANTS

Data collectors will be licensed healthcare professionals (doctors or nurses) with at least one 6-12 months of experience working in the field of paediatrics. They will be recruited after interviews with the selection team (Investigators and project manager) upon giving advertisements for posts of data collectors.

For selection of the LHWs to observe them, a randomly selected rural community through our computerized system will be generated from where the caregivers will be selected to act as disguised ones. Additionally, a complete list of functional RHCs and BHUs will be obtained from the corresponding district health office (DHO) which is the administrative authority for these centres. From that list, four BHUs and four RHCs per province will be randomly selected using a lottery method. For sampling of the practitioners, a list of tertiary care facilities will be obtained from the health department of each province and a list of private clinic and private hospitals from their corresponding directories. These lists will be used to randomly select five practitioners each from public and private sector. Once the BHU, RHC, private and public practitioner sites have been selected, disguised caregiver will be recruited and observations made. In case a healthcare provider is not available or if a facility has been closed down, the caregiver will be provided an alternate address.

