6 STUDY ASSESSMENTS

6.1 STUDY ASSESSMENTS

The following assessments will be done while doing one time observations using the observation tool (Annex A):

1. History taking: (Did the healthcare provider inquire about the presenting complaints and the predisposing factors which might have led to the complaints)
 - ✓ Cough (presenting complaint)
 - ✓ Fast breathing (presenting complaint)
 - ✓ Laboured breathing (presenting complaint)
 - ✓ Fever (presenting complaint)
 - ✓ Immunization history (Predisposing factor)
 - ✓ Breastfeeding history (Predisposing factor)
 - ✓ Overcrowding (Predisposing factor)
 - ✓ Parental smoking (Predisposing factor)

- ✓ Air pollution (Predisposing factor)
- ✓ Nutritional history (Predisposing factor)
- ✓ Hygienic practices (Predisposing factor)
- ✓ Family history of HIV (Predisposing factor)

2. Examination:

- ✓ Temperature (For fever)
- ✓ Respiratory rate for 1 minute (For fast breathing)
- ✓ Pallor (for anemia indicating malnutrition)
- ✓ Skin rash (for measles)
- ✓ Lower chest indrawing
- ✓ Auscultation for wheeze and/or crepts

3. Diagnosis:

- ✓ Cough with no fast breathing/chest indrawing: No pneumonia
- ✓ With fast breathing and/or chest indrawing : Pneumonia
- ✓ Pneumonia with any danger signs : Severe Pneumonia

4. Management:

- ✓ No Pneumonia: Symptomatic treatment
- ✓ Pneumonia: Oral amoxicillin 40mg/kg/dose twice daily for three days
- ✓ Severe Pneumonia: For LHWs: First dose of oral antibiotic (amoxicillin) and referral to health facility and for health facilities, parenteral ampicillin 50mg/kg IV 6 hourly for five days along with gentamicin 7.5mg/kg/ IM or IV for five days.

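### Section 3.5 ends the observed visit with a trip home and gives no written step when treatment or referral is missing, or when a severe case correctly managed by an LHW or BHU still needs onward referral

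*Combined protocol and SAP*

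**What the plan says.** Collectors look for real cases near pre-listed addresses (3.5). Under 4.2.1 the child "must have symptoms of pneumonia/severe pneumonia as indicated in section 6.1", so severe cases are eligible. The caregiver and child go to the provider with the collector; for an LHW, the visit may instead take place in the household (3.2).

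Section 5.1 describes the observers: "Data collectors will be licensed healthcare professionals (doctors or nurses", with paediatric experience. Section 3.4 adds training in WHO management. During the visit, "The data collector will not reveal that he/she is a healthcare professional" (3.5). Afterwards, with a one-hour limit on data entry, "Once the visit is completed, the data collector will take the caregiver back to their premises and fill up the observation tool in tablets".

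For severe pneumonia, correct care depends on the level:
- LHW (6.1): "First dose of oral antibiotic (amoxicillin) and referral to health facility".
- BHU (Annex C): "First dose of oral antibiotic (amoxicillin) and referral to rural health centre or tertiary care hospital".
- Other facilities (6.1): "for health facilities, parenteral ampicillin 50mg/kg IV 6 hourly for five days", with gentamicin.

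**The concern.** Section 1.1 says that early treatment of pneumonia saves lives and that severe cases can be fatal. The study is run because the sponsor suspects that training has not changed practice (1.2), so some inadequate care is to be expected. A trained clinician from the study team will see it happen and score it. Followed literally, 3.5 then sends the family home. An untreated child, or a severe case that an LHW or BHU has just referred, could go home with no stated next step. What happens would rest on the individual collector's judgement, and could differ between collectors and provinces.

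**Working it through.** No power or precision formula applies. The check sets the sections side by side.

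**1. Who is enrolled.** Children with real pneumonia (3.5), severe cases included (4.2.1). The only exclusion on the caregiver side is comorbidity in the child (4.2.3.1). The provider comes from a list and is not matched to severity.

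**2. What the collector knows when the visit ends.** The collector has watched the consultation, holds a copy of the prescription and an audio recording (section 7), and has a checklist that classes diagnosis and management as correct or incorrect (8.2, Annex C). The information needed to spot missing care is already in hand.

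**3. What 3.5 then requires.** Return of the caregiver and data entry. Two situations are left open:
- Needed treatment or referral was not given, at any level.
- The case is severe and the LHW or BHU acted correctly. Correct care is then a referral, so the treatment itself has yet to be given elsewhere. Section 6.1 alone does not separate BHUs from other facilities; Annex C does. This fits 3.2, which says "RHCs provide in-patient service as compared to BHUs".

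**4. Whether another section closes the gap.**

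| Section | What it does | Does it set a step for the child? |
|---|---|---|
| 3.1 | Expert input to an implementation protocol and the tool | Not stated |
| 4.1 | Same caregiver may visit an LHW, BHU and RHC where cases are few | No; it serves recruitment |
| 5.1 | Alternate address if the provider is absent or the facility closed | No |
| 5.2.1 | Withdrawal; payments that cover transport and consultation | No; it pays costs only |
| 7.2 | Key eCRF items | No safety-action item listed |
| 9.2 | Sponsor risk assessment | No |
| 11.1, 11.2 | Allow action on an immediate hazard | Permits it; sets no trigger or duty |
| 11.3 | Serious-breach notification | No |
| 11.5 | Follow-up arranged on premature closure | Only in that event |

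Adverse events appear only in the abbreviation list.

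**5. Size.** The plan's own count reproduces: 6 + 4 + 4 + 9 + 9 = 32 per location, and 32 × 5 = 160 observations (8.1). An expected number of affected children would need that count multiplied by the share of visits where needed care is missing or still to come. That share depends on case severity and provider error rates, and the plan gives neither. No estimate follows.

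**The case against.** The strongest reply is that this is an observational study that forbids no rescue. Sections 11.1 and 11.2 allow action on an immediate hazard. The caregiver knows the study's purpose and has consented, so the disguise is aimed at the provider, and nothing stops a licensed collector from advising the family afterwards. Families can be reached by phone, and transport and consultation costs are met. A safeguard may also sit in pages not available here. All of this is fair, and it bears on how strongly the point is put. But permission is not a procedure: none of these provisions says when to act, who acts or what to do.

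Several stronger readings are tempting, and the documents do not support them:
- **That care is still outstanding after every severe-case visit, including at RHCs and hospitals.** A five-day injection course does outlast a consultation, but RHCs have beds and the public practitioners work in tertiary hospitals (3.2). Admission can follow directly, and 3.5 does not say that an admitted child must be taken home.
- **That visit counts by provider type show how many children are at risk.** They count planned observations. They carry no information on severity or on care received.
- **That the study draws children away from better care.** LHWs must belong to the site's catchment (4.2.2.1), and nothing shows where the family would otherwise have gone.
- **That an action could not be recorded.** The 7.2 list gives key points only, and Annex C ends with a free-text item.
- **That the no-harm sentence in 5.2 dismisses risk to the child.** It justifies not seeking consent from providers.

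**Conclusion.** The point holds as a missing written step. For a child whose needed treatment or referral was not given at any level, and for a severe case correctly referred by an LHW or BHU, the available text states nothing beyond the trip home and data entry. Its size cannot be put in numbers. The conclusion assumes that the unavailable pages hold no such step; if they do, the remedy shrinks to a cross-reference in 3.5. It does not rest on any assumed rate of provider error, because the referral gap exists even when the LHW or BHU performs perfectly. Label: cheap improvement (patient safety).

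**What to change.** Amend 3.5 as follows.

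1. **Check after the visit.** Right after the observation and out of the provider's sight, the collector compares the care given with 6.1 and Annex C, tells the caregiver if needed treatment or referral is missing, and helps arrange it. The trigger should be missing care and not the label incorrect, since an adequate alternative regimen would also score incorrect.
2. **Danger signs.** List them from the WHO guideline behind the tool, because 6.1 names none. A child with any of them is escorted the same day, after the LHW or BHU observation, to an RHC or hospital able to give the severe-pneumonia care in 6.1, and is not taken home first. The onward visit may serve as the next observation under 4.1. Escorting after the observation keeps severe-case management by LHWs and BHUs within the primary objective; routinely diverting these children beforehand would remove much of it.
3. **Shared children.** For a child who sees several providers under 4.1, the check on non-severe care follows the last visit of each day.
4. **Record and train.** Log the action in the eCRF or the tool's free-text item. Cover the step in the 3-day training (3.4) and in the consent text.

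**Cost.** A protocol amendment, a short training item and revised consent wording, using staff and payments already planned. The downsides are collector time (an escort may press on the one-hour entry limit), a small risk of alerting providers not yet observed, and an occasional lost observation, which the additional site in 4.1 can replace.
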